- iv. There is no significant difference in means between the pre-test among the newly employed nurses (NEN) among interventional and the control groups in all dependent variables.
- v. There is a significant mean difference between PRE-SBLST and all POST-SBLST results among NEN in all dependent variables.

Study Design

The study design was a prospective, longitudinal, single-blind basic experimental design, randomized control trial (RCT) design.

Study Location

The study was carried out in Jordan; Amman and Al-Zarqa City. The accessible population was NEN in five hospitals. The researchers selected three Jordanian hospitals. The selection was according to the capacity, capability of the institution and eligibility criteria. Computer-generated randomization (Random Allocation Software, version 1.0) was applied in blocks to allocate the hospitals by distributing them into two arms. The first arm was the control group; selected from three hospitals; Prince Hamza Hospital, AL-Basheer Hospital, and AL-Zarqa Governmental Hospital (n=51); the second arm was the interventional group from two hospitals; Prince Faisal Governmental Hospital and Dr.Jameel AL-Totanji Hospital.

Randomization of the Hospitals

To prevent data contamination between the control and interventional groups, computer-generated randomization (Random Allocation Software, version 1.0) was applied in blocks to allocate the hospitals by distributing them into two arms. The first arm was the control group; selected from three hospitals; Prince Hamza Hospital, AL-Basheer Hospital, and AL-Zarqa Governmental Hospital (n=51); the second arm was the interventional group from two hospitals; Prince Faisal governmental hospital and Dr.Jameel AL-Totajji hospital. The control and interventional groups were selected from different hospitals because the researchers are always worried about data contamination and try to minimize it between the control and intervention groups; if the sample was selected from the same area and both groups worked closely together, the data would be contaminated.

Inclusion Criteria

The researchers tried to maintain homogeneity and minimize any variations among the participants by

1. selecting both interventional and control groups from newly employed nurses
2. Male and female participants
3. Participants only who understand the questionnaires and interventions in English

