4. Participants who were previously on-seat undergraduate nursing students last two years, 2020 (4th year nursing bachelor level) and 2021 (3rd year nursing bachelor level) in the period of COVID-19 pandemic and receive basic and clinical learning by online method, and now became a newly employed nurse (NEN) in hospitals and delivered care to the patient.
5. Participants can attend five to seven hours of SBLST session.
6. For more control, we selected nurses who rarely face CPR and do not attend BLS raining the last two years.

Exclusion Criteria

1. The researchers excluded the NEN participants working in intensive care units because ICU nurses face CPR and perform BLS daily.
2. Excluded participants with medical or physical health problems (e.g., pregnant women and participants complaining of lower back pain).
3. Participants who attended CPR training less than two years previously were also excluded. Finally,
4. NEN who upgraded their educational degree from a diploma to a bachelor's degree were excluded.

Research Instruments

The study consists of a pre-test, intervention, immediate post-test-1 after the intervention, and finally, the post-test-2 three months after the intervention. This study measured knowledge, practice, and confidence through pre- and post-tests in control and experimental groups. This study used two interventions: SBLST for the interventional group and AHA-BLS 2020 brochure as a standard treatment for the control group. Data collection proceeded using the Google Form Platform (A web-based instrument Copyrighted by Google application).

The evaluation process includes a pre-test and two follow-up assessments to measure knowledge, practice and confidence. The researcher will analyse the means of each test; the total dependent variables were 30 questions listed in.

Languages of the Tools

According to the HCP educational level, all four sections of the tools assessment are written in English; furthermore, the researchers' assistance clarified any misunderstanding points or need for translation to the participants.

Tools Sections

The tools consist of five sections; research information sheet and consent forms, demographical data, knowledge assessment tools, skills assessment tools, and confidence level assessment tools.

Research information sheet and Consent Forms

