Effect Size (ES) = 0.26, automatically calculated by G*Power software, depending on the sample size of the previous study, the effect size is calculated, the

Control group's post-test result $M \pm SD$ was equal (25.03 ± 3.04) with a sample size of 28 participants, and the interventional group (26.64 ± 2.64) with sample size 29 participants. The sample size is 72 participants; because the research study continued for three months, we added a 10% drop rate for each month, so the drop rate is 30%. Final sample size estimation including drop rate ($n \setminus (1 - \text{dropout rate}) = 72 / (1 - 0.30) = 102$ participants, the intervention group arm is 51 participants, and The largest sample size was obtained from the interventional group, more than the Control Group and the Control group arm 51 participants.

Simple Random Sampling of the Participants

After obtaining ethical approval and permission to conduct the study from the Ministry of Health in Jordan, approval letter (Education/Info\ 15177) and ethical approval letter (MOH/REC/2022/340), The researchers started the formal face-to-face visits to arrange with the nursing director and a continuous education office in the selected hospitals about the study objective and how the study would proceed; The researchers received the activation letter to initiate the study and prepared the list of the available participants who met the study's eligibility criteria. The number of participants depends on the availability of newly employed nurses in the institution who meet the inclusion criteria. The researchers randomly selected the participants from the participants' list by randomly sampling from newly employed nurses in each hospital for interventional and control groups.

. The response of the control group hospitals was as the following; the nursing director and continuous education in AL-Zarqa Governmental Hospital responded by providing all the information about participants and selecting a time and day to perform the Pre-test, standard treatment and the immediate post-test. Prince Hamzah Hospital and AL-Basheer Hospital gave the researcher the names of departments in the

hospital, including those with NEN, and we visited these departments to select the available NEN randomly and performed Pre-test, standard treatment, and immediate post-test in their departments.

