The response of the interventional group hospitals was as the following; Prince Faisal Governmental Hospital and Dr.Jameel AL-Totanji Hospital scheduled many days and times to perform the intervention, and the hospitals arranged with the available participants who met the eligibility criteria; then, the researcher selected the participants randomly.

Ethical Considerations

Permission to Conduct the Study

Regarding ethical considerations, approval for the study was obtained from the Human Research Ethics Committee (HREC), Universiti Sains Malaysia (USM). Moreover, ethical approvals to initiate SBLST intervention in Jordanian Hospitals in Amman and AL-Zarqa city were obtained from the Ministry of Health in Jordan; the study protocol was revised and approved for implementation by Jawatankuasa Etika Penyelidikan Manusia Universiti Sains Malaysia (JEPeM-USM) with study protocol code USM/JEPeM/22110681, which compliance with the Declaration of Helsinki, International Conference on Harmonization (ICH) Guidelines, Good Clinical Practice (GCP) Standards, Council for International Organizations of Medical Sciences (CIOMS) Guidelines, World Health Organization (WHO) Standards and Operational Guidance for Ethics Review of Health-Related Research and Surveying and Evaluating Ethical Review Practices, EC/IRB Standard Operating Procedures (SOPs), and Local Regulations and Standards in Ethical Review.

Subject Vulnerability

There is no vulnerability group in this study. All the participants were nurses over 20 years old and working in hospitals; no participants had handicaps or physical problems. The participants made the voluntary choice to take part in the trial. The researchers discussed the study's objectives, methods, benefits and risks. The study was free from any potential hazards or adverse effects on participants, no intervention was applied in emergencies, and no medicine product will be used in this study. The procedure was simple, the devices used in the intervention were safe, and the investigator was instructed to frequently ask the participant about health and physical condition, especially during chest compression.

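### Nurses appear to have been selected after their hospital's arm was known, from available staff and by routes that differ largely by arm, and the planned post-test t-tests are unadjusted.

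*Protocol*

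**What the plan says.** **Allocation.** Protocol, Study Location and Randomization of the Hospitals: "Computer-generated randomization (Random Allocation Software, version 1.0) was applied in blocks to allocate the hospitals by distributing them into two arms". Three hospitals are control and two are SBLST.

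**Sampling claim.** Protocol, Simple Random Sampling of the Participants: after the site visits the researchers "prepared the list of the available participants who met the study's eligibility criteria", and "The researchers randomly selected the participants from the participants' list by randomly sampling from newly employed nurses in each hospital", for both arms. The number taken was not fixed in advance: "The number of participants depends on the availability of newly employed nurses in the institution who meet the inclusion criteria".

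**Account by hospital, same section.**
- AL-Zarqa Governmental Hospital (control) supplied the participant information and chose the time and day.
- The other two control hospitals supplied the names of departments. The researchers write that "we visited these departments to select the available NEN randomly", and the pre-test, brochure and first post-test were done in those departments.
- At both SBLST hospitals, days for the intervention were scheduled and "the hospitals arranged with the available participants who met the eligibility criteria". The researcher's random selection came after that.

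**Time demanded.** Inclusion criterion 5 reads "Participants can attend five to seven hours of SBLST session". Under Intervention, SBLST takes 5 to 7 hours and reading the brochure takes 30 to 60 minutes.

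**Analysis.** The SAP plans independent t-tests between arms on pre-test and post-test scores, and a repeated-measures ANOVA over all tests. It names no covariates.

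**The concern.** When whole hospitals are randomised, the arms are protected from selection bias only if the nurses are identified in a way that does not depend on the arm. Here the recruitment account already sorts hospitals by arm, and the pool is staff who were available. Availability need not mean the same thing in each arm. A nurse released for a training day of 5 to 7 hours may be more motivated or less busy than a nurse met in her department for a brochure of 30 to 60 minutes. Any such difference in ability or motivation would be counted as an effect of SBLST in an unadjusted post-test comparison.

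**Working it through.** No figure in the plan tests this point directly, so the main check sets the passages against each other.

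**1. Was the arm known at selection?** At the SBLST hospitals, days for the intervention itself were scheduled before the researcher selected nurses. At two control hospitals, nurses were selected and given the brochure in the departments visited. The documents describe no concealment, no recruiter blind to arm and no enrolment before allocation was disclosed. The design is called single-blind without saying who is blinded. Knowledge of the arm is strongly implied but not stated.

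**2. Does the account fit sampling from a list?**

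| Hospitals | Arm | What the researchers received | Where selection took place |
|---|---|---|---|
| AL-Zarqa | Control | Participant information, day set by hospital | Not described beyond the general claim |
| Two others | Control | Department names | On department visits, among available nurses |
| Both SBLST sites | SBLST | Available eligible nurses arranged by hospital | After that arrangement |

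Department names are not a list of nurses, so the second row does not fit the general claim. For all five hospitals the list size, the random method and the person who applied it are not given. The routes differ between hospitals and largely, but not wholly, by arm.

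**3. Does the planned analysis protect?** The post-test t-tests carry any shift in full. The ANOVA includes the pre-test, so its group-by-time contrast would largely cancel a stable difference in ability. It would not cancel a difference in how much nurses learn or retain, such as one driven by motivation. The SAP does not name that contrast as the deciding test. Sample Size Estimation uses the between-factors test, and in a group effect averaged over time a stable shift remains.

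**4. How large could it be?** Inputs from Sample Size Estimation: control 25.03 (SD 3.04, n = 28), intervention 26.64 (SD 2.64, n = 29).
- Pooled SD = √[(27 × 3.04² + 28 × 2.64²)/55] = √(444.67/55) = 2.843.
- d = (26.64 − 25.03)/2.843 = 1.61/2.843 = 0.566, or about 0.57. As f = d/2 this is 0.28, against the stated 0.26.
- Assumed shift of 0.1 SD: 0.1/0.566 = 18%. Assumed shift of 0.3 SD: 0.3/0.566 = 53%.
- If the stated 0.26 is read as f, then d = 0.52 and the range is 19% to 58%.

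For a two-sided 5% t-test with 51 per arm, the noncentrality is b√(51/2) for a shift of b SD. Treating nurses as independent and taking no true effect:

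| Assumed shift (SD) | Noncentrality | Chance of p < 0.05 |
|---|---|---|
| 0.1 | 0.50 | 8% |
| 0.2 | 1.01 | 17% |
| 0.3 | 1.51 | 32% |

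The same figures are the power of the planned pre-test comparison to detect such an imbalance. At 0.3 SD it would miss it about two times in three, so a non-significant pre-test result is weak reassurance.

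**The case against.** The strongest reply is that the protocol asserts random selection three times: in its general statement, for the two department-visit hospitals and for both SBLST hospitals. It also says that a list was prepared. A reader might infer that random sampling did not take place, and the documents do not support that. They show a method that is undocumented and inconsistently described, which is less than proof that it was absent.

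A reader might also infer a clean split of route by arm, or take it as fact that all 102 nurses were chosen with the arm known. Neither is established. AL-Zarqa, a control hospital, used a route close to that of the SBLST hospitals. The general statement mentions the list before the hospitals' responses, without saying whether the arm had been disclosed by then.

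Criterion 5 is listed for the whole study, so on paper control nurses also had to be free for 5 to 7 hours. That weakens the argument from time burden. However, nothing shows that the criterion was checked among nurses met on department visits, whereas the SBLST schedule enforced it.

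Finally, the plan does compare pre-test scores, and its ANOVA includes the pre-test. This protection is real but partial, for the reasons in step 3 of the working.

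**Conclusion.** The concern holds in a limited form. Selection appears to have followed allocation, drew on available staff, and used routes that differ between hospitals and largely by arm. The list-sampling claim has no documented mechanism and does not fit the account of two control hospitals. Selection bias therefore cannot be excluded, and the post-test t-tests have no protection against it.

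The size is unknown. The figure of 18% to 53% of d = 0.57 rests wholly on an assumed shift of 0.1 to 0.3 SD, for which the documents give no anchor. It describes the unadjusted post-test comparison and not the group-by-time contrast. The documents do not show that bias occurred, or its direction.

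**What to change.** 1. **SAP, Inferential Statistics.** Replace the unadjusted post-test t-tests with a between-arm comparison adjusted for the pre-test score and the baseline items already collected under Demographical data: CPR exposure, previous simulation BLS training, BLS certificate and work experience.
2. **Protocol, Simple Random Sampling of the Participants.** Replace the label with the method actually used at each hospital. Report eligible, approached and enrolled counts per hospital where available. Say whether the 5 to 7 hour criterion was applied to control nurses.
3. **Limitations.** State that adjustment cannot remove unmeasured differences such as motivation or workload.

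A list of eligible nurses frozen before the arm is disclosed would help only any further recruitment. The sessions ran from November 2022 to January 2023, and post-test-2 response rates are already reported. The cost is a little more analysis work and a more cautious conclusion. No extra participants are needed.

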DEVELOPMENT, VALIDATION, AND
EVALUATION OF THE EFFECTIVENESS OF
SIMULATION IN BASIC LIFE SUPPORT TRAINING
(SBLST) ON NEWLY EMPLOYED NURSES IN
GOVERNMENTAL JORDANIAN HOSPITALS

Statistical Analysis Plan

Last update On 20-4-2023

Malaysian Human subjects protection review board date: 20-4-2023

Statistical Analysis Plan

Introduction

The data will be collected through the Google Forms platform, and the researchers will extract the data responses from Google Forms as an Excel sheet (Microsoft Office 2016); all the quantitative data will be coded and transferred to IBM SPSS version 27; the data will be analyzed by using (1) descriptive and (2) inferential statistic.

1. Descriptive Statistics

The descriptive statistic will illustrate the homogeneity and characteristics of NEN in the control and experimental group, including the number and percentage of participants for each group. Also, it will be used to describe statistics for participants' knowledge, practice and confidence level mean percentage in the pre-test and post-test scores.

2. Inferential Statistics

A. Independent T-test

Independent T-test will be used to identify the homogeneity or heterogeneity between pre-tests and post-tests in the control and experimental groups in all dependent variables by interpreting the *P*-value and comparing means (SD). The researchers plan to use independent T-tests despite the normality assumption not being fulfilled depending on the central limit theorem, which states that if samples are more than 30 participants in each group, the researcher can use mean and SD.

B. Repeated Measures-ANOVA

The researchers will use "Repeated Measurement ANOVA" for inferential statistics of the mean of the dependent variables between the interventional and comparator groups in all pre-test and post-tests. Finally, the researchers compared the

*

“Mean,” “Standard Deviation,” and significant level (*P*-value) between tests to explore the effectiveness of the intervention SBLST.

In this step of the analysis, the researchers want to estimate a good idea about the outcomes and how SBLST is considered a good intervention or not after comparing the knowledge score, practice score, and confidence level in both interventional and control groups. The researchers selected a *P*-value < 0.05 for statistical analysis significant to accept the alternative hypothesis or reject the null hypothesis.

C. Effect Size (Cohen’s Score)

The researchers will calculate the effect size between pre-test and post-test-2 in each group and identify the most effective treatment method that increases knowledge, practice and confidence score. Effect size reflects the SBLST's effectiveness if it produces a small, moderate or large effect. The researchers plan to use Cohen’s formula (d) to calculate the effect size; effect size assists the researcher in interpreting the effectiveness of the SBLST before and after intervention and also interpret the two intervention in two groups after the intervention, according to the following category (<0.2), small effect; (0.2-0.8), moderate effect, (>0.8), large effect; and finally more than 0.9, very large effect (La Cerra et al., 2019).

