The research information sheet is a piece of brief researcher information and contact details; it also includes subject information and a consent form with an area for the participant's signature when they are approved to participate in this study. Furthermore, the research information sheets include a participant's publication consent form.

Demographical data

Demographic parts are attached in; these data consist of dichotomous questions (Yes\NO), nominal data, ordinal data, and interval measurement questions. Nominal measurements include sex and ordinal assessment as educational level and area of experience; interval assessment questions include age and work experience. Dichotomous assessments (Yes\NO), asking if the participant previously participated in a CPR episode or observed any CPR before, if the participants had finished training the BLS using simulation previously, and if the participant gained the certification of BLS training from formal and accredited institutions previously.

Knowledge and practice

Nursing knowledge is the interaction of science and research to improve practice. Researchers use a 13-question MCQ tool to assess knowledge. Nursing practice is performing the knowledge learned before; the researchers assessed skills using a tool consisting of ten MCQ. The participants got zero for each wrong answer and one mark for each correct answer.

Confidence

Confidence is the build and accomplishment of the nursing profession through knowledge acquisition, skills, and critical thinking. Confidence is the positive feeling of faith and dependability to perform BLS without fear and free from risk to the patient. The researchers assessed confidence level using seven statements rated as a dropdown in percent value from the lowest value of 5% to the highest value of 100%.

Study Process

Pre-test

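### Prior CPR exposure, prior BLS training and work experience are collected but enter no between-group model, so an imbalance across the five allocated hospitals would go uncorrected into the post-test t-tests and between-group Cohen's d, and partly into the repeated-measures ANOVA

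*SAP*

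**What the plan says.** **What is collected.** Under Demographical data, the protocol lists a yes/no item on CPR exposure: "asking if the participant previously participated in a CPR episode or observed any CPR before". Two further yes/no items cover earlier simulation-based BLS training and BLS certificates from accredited bodies. On the numeric items it states that "interval assessment questions include age and work experience". The Pre-test section has this form completed before the intervention, so all four items are genuine baseline values.

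**What is done with it.** SAP section 1 says: "The descriptive statistic will illustrate the homogeneity and characteristics of NEN in the control and experimental group", by number and percentage. It does not list the four items by name; that they are among the characteristics described is an inference.

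**The inferential methods.**
- Section 2.A: "Independent T-test will be used to identify the homogeneity or heterogeneity between pre-tests and post-tests in the control and experimental groups".
- Section 2.B: a repeated-measures ANOVA of outcome means "between the interventional and comparator groups in all pre-test and post-tests".
- Section 2.C: Cohen's d from pre-test to post-test-2 within each group, and also a comparison of the two groups after the intervention.

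No covariate, regression or ANCOVA appears in any of them.

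**Allocation and eligibility.** Hospitals, not nurses, were allocated: three to control and two to SBLST (Protocol, Randomization of the Hospitals). Exclusion item 3 reads: "Participants who attended CPR training less than two years previously were also excluded".

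**The concern.** The protocol itself treats exposure to CPR as a determinant of BLS performance. It excludes intensive care nurses because they meet CPR daily, and for added control it selects nurses who rarely meet it. That reasoning stops at eligibility. Training or certificates more than two years old, occasional or observed CPR, and some spread in work experience remain possible, and the form asks about them.

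Earlier exposure can raise a nurse's score in two ways. It can raise the current level, which the pre-test would show. It can also speed relearning or help retention to three months, which the pre-test would not show. If one arm holds more exposed nurses, an unadjusted comparison credits or debits SBLST for it.

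With five allocated units, chance balance is weak. Recruitment also differed between sites. At two control hospitals the researchers visited departments to choose available nurses, while the SBLST hospitals arranged sessions with available nurses before selection.

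**Working it through.** **1. The plan's own effect size, used as the yardstick.** Sample Size Estimation gives post-test results of 25.03 (SD 3.04) and 26.64 (SD 2.64) and an effect size of 0.26. The difference is 26.64 − 25.03 = 1.61. On the control SD, d = 1.61/3.04 = 0.53 and f = d/2 = 0.265, which is consistent with the stated 0.26. With f = 0.2648, four measurements and an assumed correlation of 0.5 between them, the between-factors calculation returns the stated 72.

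**2. How likely is a gap of more than 20 points?** Assume equal-sized hospitals within an arm, 51 nurses per arm, prevalence p, and between-hospital SD s in prevalence.

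SD of arm difference = √[s²(1/2 + 1/3) + 2p(1−p)/51]

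With p = 0.30 (assumed):

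| s (assumed) | SD of difference | P(gap > 20 points) |
|---|---|---|
| 0 | 0.091 | 2.8% |
| 0.10 | 0.129 | 12% |
| 0.15 | 0.164 | 22% |

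Prevalence matters. Written with an intracluster correlation, the variance is p(1−p)[ICC × 5/6 + (1−ICC) × 2/51]. For p from 0.2 to 0.5, the probability is 1–4% at ICC 0, 8–15% at 0.05 and 15–25% at 0.10. For p = 0.10 the SD is √(0.09 × 0.0789) = 0.084 at ICC 0.05 and √(0.09 × 0.1186) = 0.103 at ICC 0.10, giving about 2% and 5%.

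**3. Bias in an unadjusted post-test comparison.** Bias = gap × total effect of exposure on the post-test (assumed 0.3 to 0.8 SD). For a 20-point gap this is 0.20 × 0.3 = 0.06 SD to 0.20 × 0.8 = 0.16 SD. Divided by 0.53, that is 11% to 30% of the planning effect.

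**4. What the pre-test would remove.** Suppose exposure has the same effect b on pre- and post-test, and the pre-post correlation is 0.5 (both assumed).
- A change score removes all of the bias.
- ANCOVA on the pre-test alone leaves gap × b × (1 − β), where β = (0.5 + b²v)/(1 + b²v). With 40% v 20% exposed, v = (0.24 + 0.16)/2 = 0.20.
 - b = 0.3: β = 0.518/1.018 = 0.509, leaving 0.06 × 0.491 = 0.03 SD.
 - b = 0.8: β = 0.628/1.128 = 0.557, leaving 0.16 × 0.443 = 0.07 SD.

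If exposure acts more on the post-test (0.8 v 0.2 SD) and the gap is 30 points, the change score is itself biased by 0.30 × (0.8 − 0.2) = 0.18 SD.

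**5. False-positive rates at nominal 0.05.** Simulation, 4,000 runs per row, no treatment effect, 48 v 45 completers (Protocol, Post-test), average prevalence 30%, pre-post correlation 0.5, one pre-test and one post-test, no other hospital effect.

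| Gap; effect on pre / post (SD) | Post-test t-test | Group-by-time | Group main effect | ANCOVA: pre-test + covariate |
|---|---|---|---|---|
| 20 points; 0.5 / 0.5 | 0.077 | 0.054 | 0.083 | 0.052 |
| 30 points; 0.5 / 0.5 | 0.103 | 0.050 | 0.118 | 0.055 |
| 30 points; 0.8 / 0.8 | 0.185 | 0.056 | 0.230 | 0.050 |
| 30 points; 0.2 / 0.8 | 0.202 | 0.142 | 0.131 | 0.057 |

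**The case against.** **The pre-test already deals with this.** A reader might infer that every post-test comparison is affected. The documents do not support that. The ANOVA spans the pre-test and post-tests, and one use of Cohen's d runs from pre-test to post-test-2 within each group. A group-by-time contrast and that within-group d remove whatever already shows at pre-test, and the simulated group-by-time test holds its level when exposure acts equally on both tests. What remains is that the SAP never names group-by-time as the test of effect. The sample size rests on the between-factors test, whose group main effect is not protected. The post-test t-tests and the between-group d have no protection either.

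**Eligibility leaves little to vary.** This stands in part. Inclusion item 4 restricts entry to nurses who were third- or fourth-year students in 2020–2021, which keeps work experience short. Inclusion item 6 and exclusion items 1 and 3 remove recent training, intensive care work and frequent CPR. Exclusion item 4 removes nurses who upgraded from a diploma. Sessions ran from November 2022 to January 2023, so earlier training would date from about late 2020 or before. CPR taken part in or observed outside intensive care is the most plausible remaining source of variation.

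**Every driver of the size is assumed.** True. Prevalence, hospital spread, gap and effect have no source in the documents. The 0.3 to 0.8 SD is a total effect, including the part visible at pre-test. Its upper end exceeds the planned effect of the training itself (0.53).

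**A new adjusted model after data collection adds flexibility.** Also fair. The documents are dated 20-4-2023 and the protocol already reports post-test-2 response (48 and 45). This calls for a fixed list, disclosure of timing and the unadjusted result alongside. It is not a reason to leave the variables unused.

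**Conclusion.** The plan collects four plausible prognostic items at baseline and puts none of them in a between-group model. With hospitals allocated three to two, an imbalance would enter the post-test t-tests and the between-group Cohen's d in full, and the repeated-measures ANOVA in part. How far the ANOVA is affected depends on which term is read, and the SAP does not say.

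This is a risk and not a demonstrated bias. A reader might infer that the arms did differ on these items; the documents report no imbalance. Given a 20-point gap, the bias in an unadjusted post-test comparison is 0.06 to 0.16 SD (11–30% of 0.53). It falls to about 0.03 to 0.07 SD after pre-test adjustment if exposure acts equally on both tests. With 30% prevalence, a gap that large has a probability of about 3% with no hospital variation and 12–22% with the assumed hospital variation. At 10% prevalence the probability is lower.

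It would also be wrong to read covariate adjustment as an answer to allocation by hospital. It cannot remove unmeasured hospital differences or account for clustering.

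**What to change.** In SAP section 2, for each of knowledge, practice and confidence, compare the arms at post-test-1 and at post-test-2 with a linear model (ANCOVA) containing:
- the pre-test score of the same outcome, as an explicit covariate;
- a short fixed list: CPR participated in or observed, earlier simulation BLS training, BLS certificate, and work experience.

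State a rule, set without looking at outcomes, for merging or dropping yes/no items that are nearly constant or overlap heavily. Report the adjusted arm difference with the unadjusted one beside it, and give the date the list was fixed relative to data collection. Keep the descriptive table. If the repeated-measures ANOVA is retained, say which term is the test of effect.

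**Cost.** A few lines of SAP text and modest extra SPSS work; the protocol already collects all the variables through its forms. The five added terms use about five degrees of freedom. Residual degrees of freedom would be 102 − 7 = 95 with everyone at post-test-1 and 93 − 7 = 86 with the 48 + 45 completers at post-test-2. Accounting for hospital-level allocation remains a separate task.
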